9.2.4 Dose De-escalation for PLX9486 combinations

Combination with PLX3397: If ≥ 2 of the first 6 patients who receive the first dose level in Part 2b experience a protocol-defined DLT, the administration of PLX9486 and PLX3397 will be considered too toxic and dosing will be reconfigured.

PLX3397 dose de-escalation will be in decrements of 200 mg per day. Examples of these dose reductions are provided in [Table 21](#).

Table 21: PLX3397 Examples of Dose Reductions for the 600 mg Daily Dosing Cohorts

Dose Level	When
600 mg	Starting dose
400 mg	1 st dose reduction
200 mg	2 nd dose reduction
Off study	3 rd dose reduction required

Combination with sunitinib: If ≥ 2 of the first 6 patients who receive the first dose level in Part 2e experience a protocol-defined DLT, the administration of PLX9486 and sunitinib will be considered too toxic and dosing will be reconfigured as follows:

- Hold sunitinib for \geq Grade 3 drug related AEs
 - First occurrence:
 - Hold drug until AE \leq Grade 1 for non-hematologic events or AE \leq Grade 2 for hematologic events. Resume at same dose level if at 37.5 mg dose.
 - For Grade 3 treatment-related AE, dose reduce to 25 mg if at 37.5 mg or resume at reduced dose of 25 mg.

- For Grade 4 treatment-related AE, if at 25 mg dose level, hold sunitinib until AE \leq Grade 1 for non-hematologic events or AE \leq Grade 2 for hematologic events, then resume at 25 mg dose level or discontinue sunitinib
- Second occurrence:
 - Hold sunitinib until AE \leq Grade 1 for non-hematologic events or AE \leq Grade 2 for hematologic events. If at 37.5 mg, dose reduce to 25 mg, and if at 25 mg, discontinue sunitinib

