If a stable combination dose of PLX9486 and sunitinib is unattainable, dosing will be halted and a new dose configuration with a lower dose of sunitinib (e.g., 25 mg sunitinib and 150 mg PLX 9486) will be developed. For the combination parts of the study (Part 2e and [redacted]), if one study drug needs to be temporarily discontinued due to an adverse event, then both drugs need to be discontinued until the adverse event resolves per the dose modification guidelines. If one study drug needs to be permanently discontinued, then both study drugs must be permanently discontinued and the patient taken off-study.

These parameters are only a guide and are not intended to supersede the clinical judgment of the treating physician. The dose modification/reduction guidelines are for clinically significant toxicities that are at least possibly related to study drug administration. Definitions of "clinically significant" and "related" will be made based on the judgment of the investigator and the case discussed with the Medical Monitor as needed. All adjustments should be made in consultation with the Medical Monitor. Dosing interruptions longer than 2 weeks for any reason should generally result in discontinuation from the study, unless the patient has demonstrated a clinical benefit from therapy and would like to continue dosing with study drug after discussion between the investigator and the Sponsor.

Table 22: Recommended PLX9486 Dose Modifications (Including Stopping Rules)

All Drug-Related Toxicities	Frequency	When to Hold or Stop	When to Restart Dose ^a
Grade 3 or 4 neutropenia	1st Appearance	Interrupt until ANC recovers to $\geq 1 \times 10^9/L$; growth factor support permitted	If recovered to ANC $\geq 1 \times 10^9/L$ in ≤ 7 days, resume at same dose.
			If not recovered to ANC $\geq 1 \times 10^9/L$ after 7 days, reduce dose by 1 dose level.
		Interrupt until ANC recovers to $\geq 1 \times 10^9/L$; growth factor support permitted	If recovered to ANC $\geq 1 \times 10^9/L$ in ≤ 7 days, reduce dose by 1 dose level.
	2nd Appearance	Interrupt until ANC recovers to $\geq 1 \times 10^9/L$; growth factor support permitted	If recovered to ANC $\geq 1 \times 10^9/L$ in ≤ 7 days, reduce dose by 1 dose level.
			If not recovered to ANC $\geq 1 \times 10^9/L$ after 7 days, reduce dose by 2 dose levels.

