Detailed medical history and physical examination seeking new abnormalities.	Evaluate abnormalities found.
Full serological evaluation for hepatitis A, B, C, and E (IgG and IgM). Check for autoimmune hepatitis with serological laboratory studies.	If viral hepatitis or autoimmune hepatitis suggested, have patient evaluated by hepatologist.
Liver ultrasound performed to evaluate liver and biliary tree.	Evaluate any abnormalities found.
Check history for exposure to chemical agents.	Remove chemical exposure and have patient seen by hepatologist.
Obtain hepatology consult if liver function continues to rise beyond 14 d.	Contact Medical Monitor.
We request that cases be discussed with the Medical Monitor as defined in the protocol whenever investigational product is being held for liver function test abnormality.	

Ig = Immunoglobulin; INR = international normalized ratio; OTC = over-the-counter

For suspected cases of cholestatic liver injury (e.g., aminotransferase increase concurrent with hyperbilirubinemia, or liver biopsy suggesting cholestasis and/or ductopenia), patients will be followed to assess long-term outcome. Additional diagnostic and follow-up procedures might be implemented as appropriate to fully assess the event.

Sunitinib Dose Modification Guidelines:

For all sunitinib drug modifications, see [Section 9.2.4](#). For further guidance, consult the package insert.

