10.3 Treatment Group Assignments

This is an open-label, sequential dose-escalation study with extension cohorts. The initial dose level of PLX9486 will be 250 mg/day. Thereafter, dose-escalation groups will occur as described in [Section 9.2.1](#). Extension cohorts will be enrolled in parallel at the RP2D according to inclusion and exclusion criteria ([Section 8.1](#) and [Section 8.2](#)). The initial dose of PLX3397 will be 600 mg/day administered BID. Thereafter, dose escalation groups will occur as described in [Section 9.2.1.2](#). For the combination cohort with sunitinib the initial sunitinib dose will be 25 mg/day. Further details may be found in [Section 9.2.1.2](#).

10.4 Withdrawal of Patients from Drug Treatment or from the Study and Patient Replacement

The Plexxikon Medical Monitor will monitor safety data throughout the course of the study. The Medical Monitor will review SAEs within timeframes mandated by company procedures and will review trends, laboratory data, and AEs at periodic intervals and provide for interim safety analyses if appropriate.

The reasons a patient may discontinue or be withdrawn from the study include, but are not limited to, adverse event, clinically significant disease progression, patient request, investigator decision, protocol violation, patient noncompliance, and study termination by the Sponsor or institutional review board (IRB)/independent ethics committee (IEC). When a patient discontinues or is withdrawn, the investigator will notify the Sponsor and should perform the procedures indicated in the End of Study column in the Schedule of Events within 30 days after discontinuation of study drug and before initiation of any new anti-cancer therapy. Follow-up information will be obtained for patients who discontinue their participation in or are withdrawn from the study.

Patients withdrawn from the study for reasons other than toxicity or clinically significant disease progression (e.g., protocol violation or noncompliance) may be replaced at the discretion of the medical monitor and the investigator. Study drug administration may be discontinued due to an adverse event or at the discretion of the investigator.

The consequence of withdrawal of consent by a patient will be that no new information will be collected from that patient and added to the existing data or any database. However, every effort will be made to follow all patients for safety.

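### Section 9.2.4 tells the same patient, after a first related Grade 3 event on 37.5 mg sunitinib, both to resume 37.5 mg and to drop to 25 mg, and gives no Grade 4 rule at 37.5 mg

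*Protocol*

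**What the plan says.** Section 9.2.4 of the Protocol holds sunitinib for related events of Grade 3 or higher until recovery to Grade 1 (non-hematologic) or Grade 2 (hematologic). It then sets the restart dose.

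- First occurrence, no grade named: "Resume at same dose level if at 37.5 mg dose".
- First occurrence, Grade 3: "For Grade 3 treatment-related AE, dose reduce to 25 mg if at 37.5 mg or resume at reduced dose of 25 mg".
- First occurrence, Grade 4: "For Grade 4 treatment-related AE, if at 25 mg dose level, hold sunitinib until AE" has recovered, then resume 25 mg or discontinue.
- Second occurrence, after recovery: "If at 37.5 mg, dose reduce to 25 mg, and if at 25 mg, discontinue sunitinib".

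The list is introduced as what happens when 2 or more of the first 6 patients "who receive the first dose level in Part 2e experience a protocol-defined DLT". Section 10.3 gives the dose at that level: "For the combination cohort with sunitinib the initial sunitinib dose will be 25 mg/day"; Table 18 agrees.

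At its end, Section 9.4 sends the reader back: "For all sunitinib drug modifications, see" Section 9.2.4, with the package insert for further guidance. Section 9.4 also says that sunitinib changes should follow the package insert, that its parameters are only a guide, and "All adjustments should be made in consultation with the Medical Monitor".

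**The concern.** The sunitinib list is a patient-safety instruction, and at 37.5 mg it cannot be followed as written. The first two first-occurrence bullets give different doses for the same Grade 3 event, and nothing links them as alternatives: no recovery time, no condition, no word such as unless.

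The Grade 4 bullet leaves out 37.5 mg. If the Grade 3 bullet is taken to override the ungraded one, the milder event leads to a reduction and the more severe event to a full-dose restart. If the ungraded bullet governs, the Grade 3 instruction at 37.5 mg has no effect. Neither reading is a coherent rule.

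The dose is a planned one: Table 18 gives 37.5 mg to Cohort 3, Section 9.2.1.2 allows intra-patient escalation, and the Synopsis says that patients are still being treated in Part 2e.

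**Working it through.** No sample size, power or error rate is involved. The check is to read 9.2.4 as a decision table and set it beside Table 22.

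**Step 1. What 9.2.4 orders after recovery.**

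| Event | At 37.5 mg | At 25 mg |
|---|---|---|
| First, Grade 3 | resume 37.5 mg (ungraded bullet) and reduce to 25 mg (Grade 3 bullet) | resume 25 mg |
| First, Grade 4 | resume 37.5 mg (ungraded bullet only) | resume 25 mg or discontinue |
| Second, any | reduce to 25 mg | discontinue |

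The 25 mg column and the second-occurrence row each give a usable instruction. The contradiction is in the Grade 3 cell at 37.5 mg. The Grade 4 cell at 37.5 mg has no instruction of its own.

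**Step 2. What Table 22 orders for PLX9486 after the same first event.**

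| First event | PLX9486 (Table 22) | Sunitinib from 37.5 mg (9.2.4) |
|---|---|---|
| Grade 3 or 4 neutropenia, or thrombocytopenia without bleeding, recovered in 7 days or less | same dose | Grade 3: 37.5 or 25 mg; Grade 4: 37.5 mg |
| Other Grade 3, recovered in 5 days or less | same dose | 37.5 or 25 mg |
| Other Grade 3, longer than 5 days | reduce one level | 37.5 or 25 mg |
| Other Grade 4, recovered in under 5 days | reduce one level | 37.5 mg |
| Other Grade 4, 5 days or longer | discontinue | both drugs stop (9.4) |

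The fourth row is the clear mismatch: one drug is cut and the other restarts at full dose. In the first row, a Grade 4 event is treated alike for both drugs.

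**Step 3. Which time window.** Section 9.3 does not allow dose reductions in the DLT window for subjects counted in escalation decisions. It also lets a subject with a DLT continue at a lower dose. The contradiction and the Grade 4 mismatch are therefore open mainly after Cycle 1.

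**Step 4. The trigger.** The list follows from DLTs at the first Part 2e dose level. Sunitinib there is 25 mg, so no patient who sets off the trigger is on 37.5 mg. The 37.5 mg lines make sense only as a rule for every sunitinib patient, which is how Section 9.4 uses them.

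**Step 5. Size of the Grade 3 contradiction**, with uninterrupted daily dosing over a 28-day cycle:

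- Per day: 37.5 − 25 = 12.5 mg; 12.5 / 37.5 = 33%.
- Per cycle: 28 × 37.5 = 1050 mg against 28 × 25 = 700 mg, a difference of 350 mg.

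**The case against.** The best defense is that 9.2.4 does not stand alone. Every adjustment goes through the Medical Monitor, a shared sponsor role; clinical judgment is preserved; and sunitinib changes should also follow the package insert, which is not available here and might fill the Grade 4 gap. This stands as a limit on harm. It does not remove the defect, because none of these provisions says which bullet governs.

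Section 9.3 also takes much of Cycle 1 out of dispute. For a counted subject with a Grade 3 event that is not a DLT, the bar on reductions points to the same dose. Likewise, a reader might cite Cycle 1 Grade 4 diarrhea that falls to Grade 2 or lower within 72 hours as an unsafe full-dose restart. That event is exempt from the DLT definition, so for a counted subject 9.3 itself calls for the same dose, and the clash is between Table 22 and 9.3.

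A reader might further infer that any same-dose restart after a Grade 4 event is wrong, so that two of the four first-occurrence cases are defective. The Protocol does not support that. Table 22 itself resumes PLX9486 at the same dose after Grade 4 neutropenia, or thrombocytopenia without bleeding, that recovers within 7 days.

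Finally, the second-occurrence line for patients at 37.5 mg might seem to show that the ungraded bullet was intended. It does not settle the matter: Section 9.2.5 permits re-escalation for sunitinib patients, so a patient could be back at 37.5 mg under either reading.

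**Conclusion.** The point holds in this form. For a first related Grade 3 event at 37.5 mg, Section 9.2.4 contradicts itself, and the two readings differ by 12.5 mg/day (33%). For a first Grade 4 event at 37.5 mg it has only the ungraded same-dose bullet, which after Cycle 1 conflicts with Table 22 for an Other Grade 4 event recovering in under 5 days. The list is also placed under a trigger at which its 37.5 mg lines cannot apply.

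This rests on the text of 9.2.4, on Section 9.4 making it the reference for all sunitinib changes, and on daily dosing for the cycle totals. Only patients with a related Grade 3 or 4 event while on 37.5 mg are affected. The Protocol does not say how many are on that dose. The Synopsis reports one DLT to date, in Part 1, and one anemia SAE possibly related to both PLX9486 and sunitinib, without grade or dose. It would go too far to infer that any patient has been misdosed. No statistical figure changes. The text should be corrected because it is a safety rule and the repair is cheap.

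**What to change.** Move the sunitinib list out from under the trigger of 2 DLTs in the first 6 patients, and state that it applies to every patient on sunitinib. Replace the conflicting first-occurrence bullets with one instruction per grade and dose.

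For a first event at 37.5 mg, hold to the recovery grade already stated, then:

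- resume 37.5 mg only where the Table 22 row for that toxicity resumes PLX9486 at the same dose;
- reduce to 25 mg where that row reduces PLX9486, including febrile neutropenia, thrombocytopenia with bleeding, and Other Grade 4;
- stop both drugs where that row discontinues PLX9486, as Section 9.4 requires;
- decide with the Medical Monitor where Table 22 gives no restart rule (transaminases).

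Keep the existing 25 mg and second-occurrence lines. Cross-refer to Section 9.3 for the bar on reductions in the DLT window and the lower-dose option after a DLT.

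A simpler rule that never restarts 37.5 mg after Grade 4, or that always restarts it after a short Grade 3 event, would create new mismatches with Table 22 and should be avoided.

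The cost is a short wording amendment. It adds no visits or procedures, but as a protocol change it needs IRB/IEC approval and submission to the regulatory authorities under Section 14.8.

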9.2.5 Dose Re-escalation after a Dose Reduction

In general, dose re-escalation is not performed in subjects who have had a dose reduction. However, for a subject receiving combination therapy with PLX9486 and sunitinib, re-escalation to the original dose level is permitted at the discretion of the investigator and after discussion with the medical monitor if the subject has not experienced any treatment-related non-hematologic AE or a Grade ≥ 2 hematologic AE during the previous cycle at the reduced dose level.

9.3 Definitions of Dose-limiting Toxicity

Dose-limiting toxicities (DLTs) are defined as AEs that occur during Cycle 1, are classified as possibly or probably related to the study drug, and meet one of the following CTCAE v4.03 criteria below. DLTs will be evaluated for each cohort and for each dosing schedule. Toxicities that occur during Cycle 2 or later will be reviewed, and their impact on dose-escalation and dosing frequency will be assessed.

In each cohort, to maximize safety, there will be a 24-hour delay between the first subject enrolled and later subjects enrolled. .

Subjects who are considered in dose-escalation decisions are not allowed dose reductions during the DLT assessment window. Subjects who withdraw from the study prior to completing Cycle 1 for any reason other than a DLT will be replaced. Patient numbers must not be re-used.

A subject who experiences a DLT may remain in the trial and continue receiving study drug at a lower dose if the investigator deems the potential benefit outweighs the risk and that the subject is not eligible for, and/or interested in, an alternative therapy after consultation with the Medical Monitor.

Hematologic Toxicities

- Grade 4 neutropenia lasting >7 days
- Grade ≥ 3 neutropenia with fever
- Grade 4 thrombocytopenia
- Grade ≥ 3 thrombocytopenia lasting more than 7 days or associated with clinically significant bleeding
- Grade 4 anemia

Other Toxicities

- Any \geq Grade 3 (AE or laboratory) toxicity despite adequate supportive care/medical management except for the following:
 - Grade ≥ 3 nausea, vomiting, or diarrhea that resolves to Grade ≤ 2 within 72 hours, with or without medical intervention or prophylaxis because this would not be considered treatment-limiting in an oncology population
 - Grade 3 fatigue that resolves to \leq Grade 2 within 14 days because this would not be considered treatment-limiting in an oncology population
 - Grade ≥ 3 asymptomatic changes in alkaline phosphatase, hypomagnesemia, hyperglycemia, or hypophosphatemia that is felt by the investigator to be clinically insignificant
 - Grade 3 asymptomatic increases in transaminases (AST, ALT) confirmed upon repeat testing which resolves to \leq Grade 2 within <5 days
- Any other Grade ≥ 3 toxicity (except those noted above) for which the Principal Investigator or Sponsor deems further dose escalation inappropriate

For both **Part 1** and **Parts 2b** and **2e**, in the absence of a DLT, patients must complete the first cycle of treatment (28 days) in order to be considered evaluable for DLT. Patients who discontinue for any reason other than a DLT or Grade ≥ 2 toxicity and have received less than 21 of 28 days of dosing will not be considered evaluable for DLT and will be replaced; however, their data will be reviewed by the study committee and a decision will be made based on their review.

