	
Secondary Objectives:
 
• To determine the PK of PLX9486 as a single agent and in combination with PLX3397 or sunitinib.• [REDACTED]• To estimate the following:
• ORR (using RECIST 1.1)• CBR (Parts 2b and e)• OS (overall survival) and 12-month OS rate• PFS and 6-month PFS rate• Duration of response (DoR) 
Exploratory Objectives:
 
• To assess biomarkers in peripheral blood and in archival tumor tissue• To assess tumor response in the Part 2 cohorts by Choi criteria (Choi 2007)
Study Design:	This Phase 1b and 2a, open-label, multicenter study includes a dose-evaluation portion (Part 1) in which the safety profile and RP2D of PLX9486 as a single oral agent administered daily in 28-day dosing cycles will be evaluated in patients with solid tumors (including GIST), followed by signal-seeking extension cohorts (Part 2) in which the following will be evaluated: [REDACTED] Part 2b. Open-label, sequential cohort dose-finding study of PLX9486 combined with PLX3397 in up to approximately 30 patients with solid tumors (including GIST) in a 3+3 design. [REDACTED] [REDACTED]

Part 2e. Open-label, sequential cohort dose-finding study of PLX9486 combined with sunitinib in up to approximately 30 patients with solid tumors (including GIST) in a 3+3 design.

A review of the safety data from the 49 patients treated over the last 4 years suggested it was appropriate to reduce the frequency of surveillance. As of 26 April 2019 the clinical safety experience with PLX9486, either alone or in combination with PLX3397 or sunitinib, can be summarized as follows:

- The most common AEs considered related to PLX9486 monotherapy, as well as PLX9486 in combination with PLX3397 or sunitinib, were fatigue, diarrhea, and nausea.
- A subject receiving PLX9486 1000 mg QD in Part 1 of Study PLX121 01 experienced the only DLT to date: a possibly related Grade 3 event of anemia. The subject's dose of PLX9486 was not changed and the event resolved.
- One SAE of anemia considered possibly related to both PLX9486 and sunitinib was reported. No other treatment-related SAEs or deaths have been reported.

Patients were enrolled in Parts 1, 2b, and e only and that as of the date of this protocol amendment patients are being treated in Parts 2b and e only.

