9.4 Dose Modification Guidelines and Stopping Rules

Toxicities that occur outside the DLT window will be taken into consideration when determining the RP2D. Reduction/interruption of dosing for AEs may take place at any time. [Table 22](#) summarizes the guidelines for dosage modification (including stopping rules) for PLX9486-related toxicities as well as guidelines for their management. Dose reductions for PLX9486 should occur in decrements of 200 mg per day and for PLX3397 should occur in decrements of 200 mg/day, depending on the toxicity grade, as noted in [Table 21](#). [Table 23](#) summarizes the guidelines for dosage modification (including stopping rules) for PLX3397-related toxicities (excluding liver function abnormalities) and guidelines for their management. [Table 24](#) summarizes the guidelines for PLX3397 dosage modifications (including stopping rules) for liver function abnormalities, and [Table 25](#) provides additional liver evaluations for the management of liver function abnormalities.

Dose reductions of one or both study drugs will be made based on the known toxicity of PLX3397 and on the specific toxicity of PLX9486, and will be made only after decision by the Sponsor's medical monitor in discussion with the investigator(s). The dose modification guidelines in [Table 22](#) are applicable to all parts of the study. Dose modifications of sunitinib should follow the USPI, as well as the guidance below.

If a stable combination dose of PLX9486 and PLX3397 is unattainable, dosing will be halted and a new dose configuration with a lower dose of PLX3397 (e.g., 600 mg PLX3397 and 150 mg PLX 9486) will be developed. For the combination parts of the study (Part 2b and [redacted]), if one study drug needs to be temporarily discontinued due to an adverse event, then both drugs need to be discontinued until the adverse event resolves per the dose modification guidelines. If one study drug needs to be permanently discontinued, then both study drugs must be permanently discontinued and the patient taken off-study.

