	3rd Appearance	Interrupt until ANC recovers to $\geq 1 \times 10^9/L$; growth factor support permitted	If recovered to ANC $\geq 1 \times 10^9/L$ in ≤ 7 days, reduce dose by 1 dose level.
			If not recovered to ANC $\geq 1 \times 10^9/L$ after 7 days, discontinue permanently.
Grade 3 or 4 febrile neutropenia	1st Appearance	Interrupt until ANC and fever recover; provide growth factor support	If recovered to ANC $\geq 1 \times 10^9/L$ and T $\leq 38^{\circ}C$ in ≤ 7 days, reduce dose by 1 dose level.
			If not recovered to ANC $\geq 1 \times 10^9/L$ after 7 days, discontinue permanently.
	2nd Appearance	Interrupt until ANC and fever recover; provide growth factor support	If recovered to ANC $\geq 1 \times 10^9/L$ and T $\leq 38^{\circ}C$, reduce dose by an additional 1 dose level.
			If not recovered to ANC $\geq 1 \times 10^9/L$ after 7 days, discontinue permanently.
	3rd Appearance	Discontinue permanently; provide growth factor support	N/A

All Drug-Related Toxicities	Frequency	When to Hold or Stop	When to Restart Dose ^a
Grade 3 or 4 thrombocytopenia without bleeding	1st Appearance	Interrupt until PLT $\geq 75 \times 10^9/L$	If recovered to PLT $\geq 75 \times 10^9/L$ ≤ 7 days, resume at same dose.
			If not recovered to PLT $\geq 75 \times 10^9/L$ after 7 days, reduce dose by 1 dose level.
	2nd Appearance	Interrupt until PLT $\geq 75 \times 10^9/L$	If recovered to PLT $\geq 75 \times 10^9/L$ in ≤ 7 days, reduce dose by 1 dose level.
			If not recovered to PLT $\geq 75 \times 10^9/L$ after 7 days, reduce dose by 2 dose levels.
Grade 3 or 4 thrombocytopenia with bleeding	3rd Appearance	Interrupt until PLT $\geq 75 \times 10^9/L$	If recovered to PLT $\geq 75 \times 10^9/L$ in ≤ 7 days, reduce dose by 1 dose level.
			If not recovered to PLT $\geq 75 \times 10^9/L$ after 7 days, discontinue permanently.
	4th Appearance	Discontinue	N/A
	1st Appearance	Interrupt until PLT $\geq 75 \times 10^9/L$ and bleeding stops	If recovered to PLT $\geq 75 \times 10^9/L$ and bleeding stopped ≤ 7 days, reduce by one dose level. If not recovered to PLT $\geq 75 \times 10^9/L$ and bleeding continues discontinue permanently.
Other Grade 3 toxicities (excluding trans-aminase increases)	1st Appearance	Interrupt until resolved (Grade 0–1); start symptomatic treatment if possible	If recovered ≤ 5 days, resume at same dose.
			If symptoms persist for >5 days despite supportive management, reduce by 1 dose level.

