	2nd Appearance	Interrupt until resolved (Grade 0–1); start symptomatic treatment if possible	If recovered ≤ 5 days, reduce dose by 1 dose level.
			If symptoms persist for >5 days despite supportive management, discontinue permanently.
Other Grade 4 toxicities (excluding trans-aminase increases)	1st Appearance	Interrupt until resolved (Grade 0–1); start symptomatic treatment if possible	If recovered <5 days, reduce by 1 dose level.
			If symptoms persist for ≥ 5 days despite supportive management, discontinue permanently.
	2nd Appearance	Discontinue permanently; start symptomatic treatment if possible	N/A

All Drug-Related Toxicities	Frequency	When to Hold or Stop	When to Restart Dose ^a
Transaminase increases	
 ALT or AST $>8 \times$ ULN ALT or AST $>5 \times$ ULN for more than 2 weeks ALT or AST $>3 \times$ ULN and Total bilirubin $>2 \times$ ULN or INR >1.5 (in absence of anticoagulation) ALT or AST $>3 \times$ ULN with the appearance of fatigue, nausea, vomiting, right upper quadrant pain or tenderness, fever, rash, and/or eosinophilia ($>5\%$). 	
Immediately hold dose and discuss with Medical Monitor.
 
Institute close monitoring. Any decision to restart after transaminases return to baseline must be discussed with the Medical Monitor.
	N/A
QTcF >500 msec or 60 msec increase from baseline verified on repeat ECG	First appearance	
Interrupt study drug until resolved.
	
Upon recovery to QTc ≤ 500 ms (Grade ≤ 2), restart at a reduced dose (at least one dose level).
 
Permanently discontinue study drug if the QTc interval remains >500 ms and increased >60 ms from pretreatment values (after controlling cardiac risk factors for QT prolongation e.g., electrolyte abnormalities, congestive heart failure, and bradyarrhythmias)^b.

Note: The guidelines in this table apply to all parts of the study.

^a See [Section 9.2](#) for dose levels.

^b QTc: Only one dose reduction is permitted per patient. Prior to and following treatment initiation or after dose modification of study drugs for QTc prolongation, evaluate ECG and electrolytes (including potassium, magnesium, and calcium) after 15 days, and monthly thereafter or more often as clinically indicated.

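### Section 9.3 gives a lower-dose route after a DLT, but Table 22 resumes the same dose after one defined DLT and some Grade 3 events, and no sentence says which governs

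*Protocol*

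**What the plan says.** **After a DLT.** Section 9.3 states: "A subject who experiences a DLT may remain in the trial and continue receiving study drug at a lower dose". The conditions are that the investigator judges benefit to outweigh risk, that the subject is not eligible for or interested in an alternative therapy, and that the Medical Monitor is consulted. The paragraph also rules out dose reductions in the DLT assessment window for subjects who count in dose-escalation decisions.

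**What is a DLT.** The hematologic list in Section 9.3 includes "Grade 4 thrombocytopenia" with no limit on duration and no bleeding condition. The general clause covers Grade 3 or worse "AE or laboratory) toxicity despite adequate supportive care/medical management", with listed exceptions. One exception is "Grade 3 asymptomatic increases in transaminases (AST, ALT) confirmed upon repeat testing which resolves to" Grade 2 or lower in under 5 days.

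**Dose modification.** Section 9.4 allows dosing to be reduced or interrupted for AEs at any time and says the Table 22 guidelines "are applicable to all parts of the study". For a first Grade 3 or 4 thrombocytopenia without bleeding, recovered in 7 days or less, the restart instruction ends "days, resume at same dose". The same instruction follows a first other Grade 3 toxicity recovered in 5 days or less. Table 23 has both rows for PLX3397. The transaminase row of Table 22 lists triggers for an immediate hold and adds: "Any decision to restart after transaminases return to baseline must be discussed with the Medical Monitor".

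**The reported case.** As of 26 April 2019 the Synopsis reports one DLT, a possibly related Grade 3 anemia at 1000 mg QD, after which the subject's "dose of PLX9486 was not changed and the event resolved".

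**The concern.** A site facing a Cycle 1 event that meets the DLT definition has two places to look. Section 9.3 describes continuation at a lower dose. The matching row of Table 22 can send the patient back to the dose that produced the event. Nothing says which passage takes precedence.

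The first stake is patient safety: like cases may be handled differently, including re-exposure to the same dose. The second is interpretive. Section 9.4 says toxicities outside the DLT window will be considered when the RP2D is determined, and the RP2D is a primary endpoint of each dose-finding part. How well a dose level is tolerated in later cycles would then depend partly on which passage was followed after a DLT.

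**Working it through.** No sample size, error rate or published figure is involved. The check sets each DLT criterion in Section 9.3 beside the Table 22 instruction for a first appearance.

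| Cycle 1 event (drug-related) | Section 9.3 | Table 22 | Result |
|---|---|---|---|
| Grade 4 neutropenia over 7 days | DLT | reduce one level | compatible |
| Grade 3 or worse neutropenia with fever | DLT | reduce or discontinue | compatible |
| Grade 3 or worse thrombocytopenia over 7 days | DLT | reduce one level | compatible |
| Grade 3 or worse thrombocytopenia with significant bleeding | DLT | reduce or discontinue | compatible |
| Grade 4 anemia; other non-exempt Grade 4 events | DLT | reduce or discontinue | compatible |
| Grade 4 thrombocytopenia, no bleeding, recovered in 7 days or less | DLT | same dose | **contradiction** |
| Non-exempt Grade 3 event, recovered in 5 days or less | DLT if it persists despite adequate care | same dose | **partial overlap** |
| Asymptomatic ALT/AST above 5 and up to 8 x ULN, 5 days to 2 weeks, no bilirubin or INR rise | DLT | no trigger met | **silence** |

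**Contradiction.** Section 9.3 puts a 7-day condition on Grade 3 or worse thrombocytopenia but none on Grade 4. A Grade 4 event that recovers within 7 days is therefore a DLT, and it falls squarely in the same-dose row of Table 22. Table 23 repeats that row, so in Part 2b it arises for both drugs.

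**Overlap.** Take Grade 3 vomiting. The exception in Section 9.3 requires improvement to Grade 2 or lower within 72 hours. Table 22 resumes the same dose if the event is back to Grade 0–1 within 5 days, which is 5 x 24 = 120 hours. If both clocks start at onset, vomiting that stays Grade 3 beyond 72 hours but recovers by 120 hours can be a DLT and still return to the same dose. That window is 120 − 72 = 48 hours.

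**Silence.** Table 24 gives Grade 3 ALT/AST as above 5 to 20 x ULN. An asymptomatic Grade 3 rise stops being exempt at 5 days. Table 22 has three kinds of trigger: above 8 x ULN; above 5 x ULN for more than 2 weeks; or above 3 x ULN with a bilirubin or INR rise or symptoms. Between 5 and 8 x ULN without those features it gives no instruction for 14 − 5 = 9 days after the event has become a DLT. In the combinations other text fills the gap. Table 24 holds PLX3397 for Grade 2 and Grade 3 rises, Section 9.2.4 holds sunitinib for related Grade 3 or worse events, and Section 9.4 then interrupts both drugs.

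**Within Section 9.3.** A subject with a DLT counts in the escalation decision. If the DLT occurs early in the 28-day window, one sentence describes continuing at a lower dose and the other bars a reduction in that window. No exemption after the DLT is written.

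**Section 9.2.4.** After a related Grade 4 event at sunitinib 25 mg, resuming at 25 mg is allowed. For a first Grade 3 event at 37.5 mg, one line resumes the same level and the next reduces. This section supplies a hold but does not settle the dose after a DLT.

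**The case against.** The best defense is that the tables do not claim to override Section 9.3. Table 22 is titled as recommended modifications, and Section 9.4 calls its parameters a guide that does not displace the physician's judgement. Both routes pass through the Medical Monitor. A specific DLT rule beside general guidance would ordinarily control. This softens the conflict, but the protocol never states that order of precedence, and the Medical Monitor works from the same conflicting text.

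Four stronger readings are tempting and are not supported.

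- **That Section 9.3 forbids the same dose.** It says a subject may continue at a lower dose. That this is the sole route is an inference from the absence of any other.
- **That every related Grade 3 event is a DLT.** The general clause is qualified by adequate supportive care. An event that resolves promptly with support is arguably outside it, which is why the second item is only an overlap.
- **That transaminases are a third contradiction.** Table 22 gives no instruction to keep dosing below its triggers, so Section 9.3 is unopposed there. The silence matters mainly for single-agent dosing. Section 5.5.1 says Part 1 is complete, and the Synopsis says patients are being treated only in Parts 2b and 2e.
- **That the reported anemia was mishandled.** The document does not say how long it lasted, whether drug was held, or which amendment applied. The bar in Section 9.3 on reductions in the DLT window could itself explain an unchanged dose.

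**Conclusion.** The point holds in limited form. There is one direct contradiction (first non-bleeding Grade 4 thrombocytopenia recovered in 7 days or less), one partial overlap (some non-exempt Grade 3 events recovered in 5 days or less) and one silence (ALT/AST above 5 and up to 8 x ULN). Section 9.3 also has two sentences that do not fit together. The one reported DLT (1 of 7 patients at 1000 mg QD and 1 of 24 in Part 1, Table 10) illustrates the ambiguity. It does not establish a deviation.

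A reader might infer that the MTD decision is distorted. It is not. Under Section 9.2.2 a DLT counts whatever dose follows, and Section 12.2 summarizes safety by the originally assigned dose. Any effect runs through later-cycle tolerability and the RP2D, and the document gives no basis for putting a figure on it.

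The conclusion assumes that Table 22 applies in Cycle 1, since nothing excludes it, and that Section 9.3 intends no unstated same-dose route. Its practical weight depends on whether more patients enter a first cycle. Table 17 still leaves cohort 4 and beyond open in Part 2b.

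**What to change.** Reconcile the two sentences in Section 9.3 with each other, and then with Tables 22 and 23 and Section 9.2.4. Place one governing sentence at the head of the tables saying which passage applies when a Cycle 1 event meets the DLT definition. Mark the affected rows: Grade 3 or 4 thrombocytopenia without bleeding, other Grade 3 toxicities, and transaminase increases. State whether the bar on reductions in the DLT window still applies once a DLT has occurred. If same-dose continuation after a DLT is intended, Section 9.3 should say so, and such patients should be identified in the DLT summary. Which clinical rule is right is for the sponsor to decide.

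The cost is a short protocol amendment and a memo to sites. No additional patients or procedures are needed.
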